Clinical Phase	Post Marketing (Marketing claims, registry, post marketing surveillance), Phase 4
Trial Registration	This study will be registered on ClinicalTrials.gov by the Sponsor
Test Article(s)	Investigational Products: ACUVUE OASYS® Brand 1-Day Contact Lenses with HydraLuxe™ Technology (AO1D) Control Products: spherocylindrical refraction with trial frame (SCR)
Wear and Replacement Schedules	Wear Schedule: Daily wear Replacement Schedule: Daily disposable
Objectives	
Intent of this study is to evaluate the visual performance of AO1D.
 
The primary objective of the study is to assess electronic LogMAR Visual Acuity (VA) under high luminance, low contrast (HLLC) and low luminance high contrast (LLHC) in subjects randomly fit with: (i) ACUVUE OASYS® 1-Day, and (ii) their best corrected trial frame spherocylindrical refraction.
 
The secondary objective is to compare Contrast sensitivity as measured through the qCSF (by Adaptive Sensory Technology's Sentio Platform details on section 1. Introduction And Background) for the same 2 testing conditions listed above.
 
Other Objective: Obtain tear film interferometry measurements with and without contact lens wear. Investigate feasibility of tear film interferometry metric correlation to visual acuity.

Study Endpoints	
Primary endpoint: electronic LogMAR VA,
 
Secondary endpoint: qCSF
 
Other observation: Tear Film Interferometry (TFI)

Study Design	
This is a bilateral, non-dispensing, randomized-controlled, 2x2 crossover, single-masked, single-site study. There will be a total of 3 visits and the study endpoints will be measured in all subjects under the two testing conditions (AO1D, SCR) sequentially in separate visits based on the randomization scheme.
 
Visit 1 (~2 hours): Wearing habitual lenses.
 
Screening,
 
Baseline evaluation: Electronic LogMAR VA, CSF, TFI with habitual lenses on.
 
Lenses off best corrected spherocylindrical refraction (SCR), with best correctable VA.
 
Slit lamp findings.
 
Visits 2, 3: Randomly assigned to (i) trial frame SCR or (ii) AO1D, repeating electronic logMAR VA, CSF, TFI

Sample Size	45 subjects enrolled 42 to complete
Study Duration	4 months from FSFV to LSLV
Anticipated Study Population	
Current soft contact lens wearers 18-35 years with -0.75 D or less of cylinder in each eye and not currently wearing AO1D
 
 • -1.00 to -6.00 (in 0.25 increments) • -6.00 to -9.00 (in-0.50 increments)

Eligibility Criteria	
Potential subjects must satisfy all of the following criteria to be enrolled in the study:
 
 1. The subject must read, understand, and sign the STATEMENT OF INFORMED CONSENT and receive a fully executed copy of the form 2. Appear able and willing to adhere to the instructions set forth in this clinical protocol 3. Between 18 and 35 (inclusive) years of age at the time of screening 4. The subject must be habitual contact lens wearers (defined as minimum 6 hours per day, 5 days a week over the last month) 5. The subject must meet all of the following three criteria: 
 a. The eyes' spherical equivalent distance refraction must be in the range of -1.00 to -9.00 D (inclusive) b. The eyes' refractive cylinder must be less than or equal to -0.75 DC c. Each eye must have best corrected visual acuity of 20/25 or better. 6. The subject must have normal eyes (i.e., no ocular medications or infections of any type) 
Potential subjects who meet any of the following criteria will be excluded from participating in the study:
 
 1. Currently pregnant or lactating 2. Any systemic disease (e.g., Sjögren's Syndrome), allergies, infectious disease (e.g., hepatitis, tuberculosis), contagious immunosuppressive diseases (e.g., HIV), autoimmune disease (e.g. rheumatoid arthritis), or other diseases, by self-report, which are known to interfere with contact lens wear and/or participation in the study 3. Use of systemic medications (e.g., chronic steroid use) that are known to interfere with contact lens wear or may impact the functioning of the tear film (e.g., Isotretinoin) 4. Any ocular allergies, infections or other ocular abnormalities that are known to interfere with contact lens wear and/or participation in the study. This may include, but not be limited to entropion, ectropion, extrusions, chalazia, recurrent styes, glaucoma, history of recurrent corneal erosions, aphakia, or corneal distortion
----------------------	---

	
 5. Any current use of ocular medication 6. Any previous, or planned (during the course of the study) ocular surgery (e.g., radial keratotomy, PRK, LASIK, etc.) 7. Any Grade 3 or greater slit lamp findings (e.g., edema, corneal neovascularization, corneal staining, tarsal abnormalities, conjunctival injection) on the Efron scale 8. Any previous history or signs of a contact lens-related corneal inflammatory event (e.g., past peripheral ulcer or round peripheral scar), or any other ocular abnormality that would contraindicate contact lens wear 9. Any known hypersensitivity or allergic reaction to contact lens care products 10. Participation in any contact lens or lens care product clinical trial within 30 days prior to study enrollment 11. Employee of clinical site (e.g., Investigator, Coordinator, Technician) 12. Current wearers of AO1D brand contact lenses
Disallowed Medications/Interventions	Per exclusion criteria
Measurements and Procedures	Electronic logMAR visual acuity, quick Contrast Sensitivity Function, Tear Film Interferometry under each of the 2 testing treatments
Microbiology or Other Laboratory Testing	No microbiology or laboratory testing required in this study. See appended work-aid for Tear Film Interferometry image analysis.
Study Termination	The occurrence of one or more Unanticipated Adverse Device Effect (UADE), or any SAE where relationship to study agent cannot be ruled out, will result in stopping further dispensing investigational product. In the event of a UADE or SAE, the Sponsor Medical Monitor may unmask the treatment regimen of subject(s) and may discuss this with the Principal Investigator before any further subjects are enrolled.
Ancillary Supplies/ Study-Specific Materials	None (non-dispensing)
Principal Investigator(s) and Study Institution(s)/Site(s)	A full list of Principal Investigators, clinical sites, and institutions is kept separately from the Study Protocol and is included in the study Trial Master File.

Figure 1: Study Flowchart

COMMONLY USED ABBREVIATIONS AND DEFINITIONS OF TERMS

ADD	Plus Power Required For Near Use
ADE	Adverse Device Effect
AE	Adverse Event/Adverse Experience
BCVA	Best Corrected Visual Acuity
BSCVA	Best Spectacle Corrected Visual Acuity
CFR	Code of Federal Regulations
CLUE	Contact Lens User Experience
COAS	Complete Ophthalmic Analysis System
COM	Clinical Operations Manager
CRA	Clinical Research Associate
CRF	Case Report Form
CRO	Contract Research Organization
CT	Center Thickness
CTP	Clinical Technical Procedure
D	Diopter
DMC	Data Monitoring Committee
eCRF	Electronic Case Report Form
EDC	Electronic Data Capture
ETDRS	Early Treatment Diabetic Retinopathy Study
FDA	Food and Drug Administration
GCP	Good Clinical Practice
HIPAA	Health Insurance Portability and Accountability Act
IB	Investigator's Brochure
ICF	Informed Consent Form
ICH	International Conference on Harmonization
IDE	Investigational Device Exemption
IEC	Independent Ethics Committee
IRB	Institutional Review Board
ISO	International Organization for Standardization
ITT	Intent-to-Treat
JJVC	Johnson & Johnson Vision Care, Inc.
LC	Limbus Center
LogMAR	Logarithm of Minimal Angle of Resolution
MedDRA [®]	Medical Dictionary for Regulatory Activities
MOP	Manual of Procedures
NB	Nota Bene (pay attention)
NIH	National Institutes of Health
OD	Right Eye
OHRP	Office for Human Research Protections
OHSR	Office for Human Subjects Research
OS	Left Eye
OU	Both Eyes
PD	Protocol Deviation
PHI	Protected Health Information

PI	Principal Investigator
PIG	Patient Instruction Guide
PQC	Product Quality Complaint
PRO	Patient Reported Outcome
QA	Quality Assurance
QC	Quality Control
SAE	Serious Adverse Event/Serious Adverse Experience
SAP	Statistical Analysis Plan
SAS	Statistical Analysis System
SD	Standard Deviation
SOP	Standard Operating Procedure
UADE	Unanticipated Adverse Device Effect
USADE	Unanticipated Serious Adverse Device Effect
VA	Visual Acuity

1. INTRODUCTION AND BACKGROUND

██████████ was able to demonstrate statistically significant differences in LogMAR VA and quick Contrast Sensitivity function (qCSF) for ACUVUE OASYS® Brand Contact Lenses 1-Day with HydraLuxe™ Technology when compared to a positive Control (ACUVUE OASYS® Brand Contact Lenses 1-Day with HydraLuxe™ Technology with an added +0.25 D) and to ACUVUE OASYS®. This study will continue the investigation looking into the visual performance of ACUVUE OASYS® 1-Day compared to spectacles, in a myopic population including high myopes, through electronic LogMAR VA (eVA), qCSF as well as other observations such as tear film interferometry (TFI).

The qCSF was developed by Adaptive Sensory Technology© which uses the AST Sentio Platform for clinical testing of contrast sensitivity.² It incorporates the qCSF algorithm aimed to improve usability and comfort, while maintaining laboratory-grade precision of the test. The AST Sentio Platform is a low-risk, class I, 510(k)-exempt device that has received CE marking for marketing in Europe and is currently in the process of obtaining FDA clearance in the United States. This newer technique was chosen for this clinical trial due to its ability to deliver precise, accurate results under different conditions within a very short time (~40 minutes) compared to existing techniques.

Tear film interferometry with contact lenses on and off the eyes will also be investigated here, in an attempt to determine the feasibility of a tear film interferometry metric correlation to visual acuity.

1.1. Name and Descriptions of Investigational Products

ACUVUE OASYS® Brand Contact Lenses 1-Day with HydraLuxe™ Technology are made of senofilcon A material, an FDA approved product.

The intended use of the investigative product is for correcting myopia. During the study, the test article will be worn bilaterally in daily wear modality for the duration of the testing sessions and will be disposed of at the end of the session.

1.2. Intended Use of Investigational Products

Not applicable. Marketed product only.

1.3. Summary of Findings from Nonclinical Studies

Not applicable, marketed product only.

1.4. Summary of Known Risks and Benefits to Human Subjects

See test article package insert and Informed Consent form.

1.5. Relevant Literature References and Prior Clinical Data Relevant to Proposed Clinical Study

2. STUDY OBJECTIVES, ENDPOINTS AND HYPOTHESES

2.1. Objectives

- The primary objective of the study is to assess electronic LogMAR Visual Acuity under high luminance, low contrast (HLLC) and low luminance high contrast (LLHC) in subjects randomly fit with:
 - (i)AO1D, and
 - (ii) their best corrected spherocylindrical refraction (Trial Frame)
- The secondary objective is to compare Contrast sensitivity as measured through the qCSF (by AST Sentio Platform's technology) for the same 2 testing conditions listed above.
- Other Objectives: Obtain tear film interferometry measurements with and without contact lens wear. Investigate feasibility of tear film interferometry metric correlation to visual acuity.

2.2. Endpoints

Primary Endpoint

- Electronic LogMAR VA under HLLC and LLHC in the 2 testing treatments: AO1D, SCR.

Secondary Endpoint

- Quick Contrast Sensitivity Function under the 2 testing treatments: AO1D, SCR

Other Observation

- Tear Film Interferometry under the 2 testing treatments: AO1D, SCR.

2.3. Hypotheses

Primary Hypotheses

HLLC and LLHC electronic logMAR Visual Acuity of ACUVUE OASYS® Brand Contact Lenses 1-Day with HydraLuxe™ Technology (AO1D) will be non-inferior to that of best corrected spherocylindrical refraction with trial frame (SCR). A non-inferiority margin of 0.05 (2 and half letters) is assumed.

Secondary Hypotheses

The area under log of the contrast sensitivity function will not be statistically different for ACUVUE OASYS® Brand Contact Lenses 1-Day with HydraLuxe™ Technology compared to best corrected spherocylindrical refraction.

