14.2. Sample Size Justification

There will be one testing site: VRC [REDACTED] A total of approximately 45 eligible subjects will be enrolled into the study at this site. At least 42 subjects will complete this study. The sample size to complete the study is based on the primary hypothesis selected based on the results of a prior Repeatability & Reproducibility (R&R) study regarding ETDRS visual acuity test. The R & R study is a post-hoc analysis of two studies CR-1619 and CR-1622.

Using the POWER procedure in SAS 9.4, below is the summary of sample size required based on the different assumptions of the true difference in electronic LogMAR visual acuity. The sample size was calculated for the non-inferiority tests with at least 90% of statistical power and 2-sided type I error of 0.05. The intraclass correlation was assumed to be 0.5.

Assuming the true difference in electronic LogMAR visual acuity is between 0 (no difference) to 0.02 (one letter), it requires 24 to 63 independent eyes to demonstrate non-inferiority.

- Electronic LogMAR visual acuity

Difference (Test-Control)	Estimated Standard Deviation	# of eyes needed	Power
0.00	0.08	24	0.9
0.02	0.08	63	0.9

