14.5. Primary Analysis

Electronic LogMAR Visual Acuity will be analyzed on the analysis population using a linear mixed model. The model will include the experimental design factors: visit, test condition (AO1D/SCR), sequence of the test conditions as fixed effects. Subject will be included as a random effect. Age and gender will be included as fixed covariates when appropriate. The covariance between residual errors from the same subject across test conditions for the same test method will be selected based on the finite-sample corrected Akaike's Information Criterion³. Covariance structures considered may include: Homogenous compound symmetry (CS) and Unstructured covariance structure (UN). The structure that returns the lowest Akaike Information Criteria Corrected (AICC) will be selected as the structure that best fit the data.

Comparisons among the test conditions will be carried out using 95% confidence intervals constructed of pairwise least-square means (LSM) differences from the linear mixed model. Non-inferiority will be established if the upper confidence limit is less than 0.05. If non-inferiority is attained, superiority will be tested. Superiority will be concluded if upper confidence limit is less than 0.

In all models, the Kenward and Roger method (Kenward and Roger, 1997)⁴ will be used for the calculation of the denominator of degrees of freedom.

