14.6. Secondary Analysis – Quick Contrast Sensitivity

The area under the contrast sensitivity function curve will be analyzed on the analysis population using a linear mixed model. The model will include the experimental design factors: test method (qCSF), visit, test method by period interaction, test condition (AO1D/SCR), sequence of the test conditions, and test method by test condition interaction as fixed effects. Subject will be included as a random effect. Age and gender will be included as fixed covariates when appropriate. The covariance between residual errors from the same subject across test conditions for the same test method will be selected based on the finite-sample corrected Akaike's Information Criterion (Keselman et al. 1998)³. Covariance structures

considered may include: Homogenous compound symmetry (CS) and Unstructured covariance structure (UN). The structure that returns the lowest Akaike Information Criteria Corrected (AICC) will be selected as the structure that best fit the data.

Comparisons among the test conditions for each test method will be carried out using 95% confidence intervals constructed of pairwise least-square means (LSM) differences from the linear mixed model. Statistically significant difference will be established if the lower confidence limit is above 0 or the upper confidence limit is less than 0.

In all models, the Kenward and Roger method (Kenward and Roger, 1997)⁴ will be used for the calculation of the denominator of degrees of freedom.

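### The secondary hypothesis predicts no statistical difference in contrast sensitivity, but the plan only tests for a difference, with no margin, similarity rule or power

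*Combined protocol and SAP*

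**What the plan says.** Section 2.3 states the secondary hypothesis for AO1D versus trial-frame spherocylindrical refraction: "The area under log of the contrast sensitivity function will not be statistically different". No margin follows it.

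Section 14.6 analyses the area with a linear mixed model and 95% confidence intervals for least-squares mean differences. Its only decision rule is: "Statistically significant difference will be established if the lower confidence limit is above 0 or the upper confidence limit is less than 0". It does not say what may be concluded when the interval includes 0.

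The matching objective in section 2.1 is more modest: "The secondary objective is to compare Contrast sensitivity as measured through the qCSF".

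On size, section 14.2 says: "The sample size to complete the study is based on the primary hypothesis". Its inputs (SD 0.08, true difference 0 or 0.02) are for logMAR visual acuity only.

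The primary endpoint is handled differently. Section 2.3 says "A non-inferiority margin of 0.05 (2 and half letters) is assumed", and section 14.5 supplies the rule that goes with it: "Non-inferiority will be established if the upper confidence limit is less than 0.05".

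**The concern.** A hypothesis of no statistical difference, paired with a test that can only establish a difference, reverses the burden of proof. The only result consistent with the hypothesis is a CI that includes 0, and fewer completers or noisier measurements make that result more likely even when the two corrections truly differ.

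An interval including 0 could then be reported as confirming that contrast sensitivity with the lens does not differ from that with trial-frame correction. The synopsis places the study in a post-marketing phase that includes marketing claims, so such a statement could well be used. The planned analysis would not support it.

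**Working it through.** **The plan's own figures.** None exists for AULCSF. The only sample sizes in section 14.2 are 24 and 63 independent eyes, for visual acuity. They reproduce with a paired t non-inferiority calculation: SD of the difference 0.08 × √(2 × (1 − 0.5)) = 0.08, margin 0.05, true difference 0 or 0.02, 90% power, one-sided 5%. They say nothing about AULCSF.

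**Inputs for the illustration**
- n = 42 completers, or 45 if all enrolled subjects complete (sections 4.3 and 14.2).
- Two-sided 95% CI, difference declared if it excludes 0 (section 14.6).
- Assumption: one paired AULCSF difference per subject, with SD s. The documents give neither s nor an important AULCSF change, so results are in units of s.
- Assumption: degrees of freedom n − 2, for a 2×2 crossover with two sequences (40 or 43).

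**Precision.** The expected half-width is t(0.975, df) × s/√n.
- n = 42: 2.021 × s/6.481 = 0.312s
- n = 45: 2.017 × s/6.708 = 0.301s

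**Chance that the interval includes 0 when a real difference δs exists.** With F the noncentral t distribution function and noncentrality δ√n, this is F(t) − F(−t). For n = 42 and δ = 0.3, the noncentrality is 0.3 × 6.481 = 1.944 and the probability is 0.525.

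| True difference | n = 42 | n = 45 |
|---|---|---|
| 0.2s | 0.756 | 0.741 |
| 0.3s | 0.525 | 0.497 |
| 0.4s | 0.284 | 0.254 |
| 0.5s | 0.115 | 0.094 |

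Power to detect a difference reaches 80% at 0.443s (n = 42) or 0.427s (n = 45).

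**Sensitivity to the unit of analysis.** qCSF is measured one eye at a time. If the 0.5 intraclass correlation in section 14.2 is taken as the correlation between eyes, 84 eyes are worth 84/(1 + 0.5) = 56 independent ones. In units of an eye-level SD, the interval then includes 0 with probability 0.69, 0.40 and 0.16 at differences of 0.2, 0.3 and 0.4 SD.

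**What a real similarity claim would need** (n = 42, 40 df, true difference 0):

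| Rule | Power, margin 0.4s | Power, margin 0.5s | Margin for 80% power |
|---|---|---|---|
| Non-inferiority, 95% CI limit | 72% | 89% | 0.44s |
| Equivalence, 95% CI within ±margin | 43% | 77% | 0.51s |
| Equivalence, 90% CI within ±margin (two one-sided 5% tests) | 63% | 88% | 0.46s |

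**The case against.** The strongest reply is that the plan does not contain the faulty conclusion. Section 14.6 allows only a finding of difference, section 2.1 only sets out to compare, and no passage says that a non-significant result shows sameness. Read literally, section 2.3 predicts a test result, and the harm depends on how a future report is written. This stands in part: the misreading is an inference from sections 2.3 and 14.6 taken together, and the section 14.6 estimate is sound. But results are judged against the pre-stated hypothesis, and this one is met by any interval that includes 0.

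Sizing a trial on its primary endpoint is ordinary practice. That is true, and it matters here only because the secondary hypothesis has the form of a similarity claim. The introduction also reports that an earlier study found significant qCSF differences, including against a +0.25 D positive control. That suggests the measure is not insensitive, but it gives no power for this comparison.

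The magnitudes are in units of an unknown s, so nobody can say whether 0.3s matters clinically. This stands, and the figures are illustrative only. The eye-level reading gives lower probabilities and the 90% CI rule gives higher equivalence power; both are shown above, and neither supplies the missing margin or rule.

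Finally, the hypothesis could be reworded as a two-sided comparison instead of deleted. That would also serve, provided the bar on no-difference claims is added.

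**Conclusion.** The concern holds. The fault lies in the hypothesis sentence of section 2.3, not in the section 14.6 estimate. The documents alone show that the secondary hypothesis is met by any 95% CI that includes 0, and that AULCSF has no margin, similarity rule or power. No numerical assumption is needed for that.

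The size is illustrative. With one paired difference per subject and 42 completers, a true difference of 0.3s would leave the hypothesis apparently confirmed in about half of trials, and 80% power to detect a difference is reached only at about 0.44s. The primary visual acuity claim is unaffected. The change should be made, but it does not threaten the trial's main conclusion.

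**What to change.** Delete the secondary hypothesis sentence from section 2.3. Keep the least-squares mean difference with its 95% CI in section 14.6 as an estimate, which serves the section 2.1 objective. Add one sentence to section 14.6: a confidence interval that includes 0 will not be reported as showing no difference or equivalence.

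This is one sentence out and one in, with no change to the analysis or sample size and no new figure. It does have to go through as a protocol amendment under section 18.3.

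If the sponsor wants a similarity claim, it must instead do the following before any outcome data are reviewed:
- say whether the question is two-sided equivalence or one-sided non-inferiority;
- justify an AULCSF margin and state the matching CI rule;
- supply an estimate of s and the power at n = 42.

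That route costs more, and 42 completers may be too few for the margin chosen.

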3. TARGETED STUDY POPULATION

3.1. General Characteristics

Forty-five (45) experienced contact lens wearers between 18 and 35 (inclusive) years who are not current wearers of (AO1D) will be recruited for this study.

